7.1 Primary Efficacy Analyses

7.1.1 *Psoriasis Area and Severity Index*

Disease activity will be assessed by the Psoriasis Area and Severity Index (PASI) which derives a score for the severity of psoriatic lesions by evaluating erythema, induration, and scaling in each of 4 body regions, as detailed in [Appendix C](#).

The primary endpoint is the proportion of subjects achieving $\geq 75\%$ reduction in PASI score (PASI-75) at Week 12.

The proportion of subjects achieving PASI-75 will be summarized for each post-dose timepoint by treatment group. The primary efficacy analysis will compare the proportion of subjects achieving PASI-75 at Week 12 between each active treatment and placebo using the CMH method as described in [Section 7](#). This analysis will be repeated at Weeks 4 and 8.

The absolute value, change and percent change from baseline in PASI score will be summarized using descriptive statistics by timepoint and treatment group. Additionally, the difference in the change from baseline between each active treatment and placebo will be assessed using ANCOVA model as described in [Section 7](#). The analysis will be repeated with percent change from baseline as the dependent variable. Estimates of least-squares (LS) means, SEs, 2-sided 95% CIs and p-values will be presented by treatment group for Weeks 4, 8 and 12.

Absolute PASI scores and the proportion of subjects achieving PASI-75, PASI-90, PASI-100, PASI-50 will also be plotted over time by treatment. The proportion of subjects achieving PASI-50, PASI-75, PASI-90 and PASI-100 at Week 12 by treatment will be presented using a bar chart. The percent reduction in PASI at Week 12 for each individual subject will be presented by waterfall plot. Each treatment group will be presented on a separate plot.

7.2 Secondary Efficacy Analyses

7.2.1 *Psoriasis Area and Severity Index*

To compare the proportion of subjects achieving PASI-75 at 12 weeks among the active treatment groups, the adjusted treatment difference, its associated 95% CI, and two-sided p-value will be presented for all 1:1 treatment comparison using the CMH method.

Time to achievement of each PASI endpoint will also be summarized using descriptive statistics and Kaplan-Meier curves .

7.3 Psoriasis Body Surface Area

Measurement of psoriasis body surface area (BSA) involvement is a continuous variable and estimated using the handprint method with the size of a patient's handprint representing $\sim 1\%$ of body surface area involved.

The absolute value and change from baseline in %BSA will be summarized using descriptive statistics by timepoint and treatment group. The absolute value and change from baseline in %BSA will be summarized using descriptive statistics by timepoint and treatment group. Additionally, the difference in the change from baseline between each active treatment and placebo will be assessed using ANCOVA model as described in [Section 7](#). Estimates of least-squares (LS) means, SEs, 2-sided 95% CIs and p-values will be presented by treatment group for Weeks 4, 8 and 12. The absolute value and change from baseline in %BSA over time will be plotted by treatment.

7.4 Physician's Global Assessment

Efficacy will also be assessed by the static Physician's Global Assessment (sPGA) and the scoring system is presented in [Appendix D](#). The frequency and percentage of subjects for each discrete sPGA score (0 through 5) will be summarized by timepoint and treatment group. The proportion of subjects who achieve a sPGA response (defined as sPGA score of "0" ("cleared") or "1" ("minimal")) will be summarized for each post-dose timepoint by treatment group. The adjusted treatment difference in proportion of subjects with a sPGA response of 0 or 1 for each active treatment compared to placebo, its associated 95% CI, and two-sided p-value will be presented for Week 4, 8 and 12 using the CMH method.

Bar charts of the proportion of subjects with the following sPGA scores will be plotted by treatment for each visit: 0, 0/1, 1, 2, 3, 4, 5.

7.5 Patient-Reported Outcomes

Quality of life (QoL) will be assessed by the following patient-reported outcomes (PRO): the Dermatology Life Quality Index (DLQI), the EQ-5D-5L, and the pruritus numerical rating scale (NRS). The two questions collected in NRS questionnaire will be assessed separated as the average itch within the past 24 hours and the worst itch within the past 24 hours. Since the EQ-5D-5L value sets used to calculate the index score are country-specific and there currently are none available for Czech Republic where some subjects are enrolled in this study, the value set for Poland will be used instead as the closest Eastern European country with available scoring instrument.

DLQI score, NRS average and worst itch scores, and the EQ-5D-5L index score are continuous variables, and the absolute value, change and percent change from baseline in each PRO assessment will be summarized using descriptive statistics by timepoint and treatment group. The absolute value, change and percent from baseline for each PRO measure will be summarized using descriptive statistics by timepoint and treatment group. Additionally, the difference in the change from baseline between each active treatment and placebo will be assessed using ANCOVA model as described in [Section 7](#). The analysis will be repeated with percent change from baseline as the dependent variable. Estimates of least-squares (LS) means, SEs, 2-sided 95% CIs and p-values will be presented by treatment group for Weeks 4, 8 and 12. The absolute value over time will be plotted by treatment for the EQ-5D-5L index score, the DLQI score, the NRS average itch and worst itch scores.

Additionally, a responder analysis will be conducted for DLQI where a responder is defined as the subject who achieved a post-baseline score of 0 or 1.

A responder analysis will also be conducted for NRS questionnaire where a responder is defined as a subject who has achieved a post-baseline itch score of < 4.

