5.2. Inclusion Criteria

Patients who meet the following criteria will be considered eligible to participate in the clinical study:

1. Able and willing to provide signed informed consent to participate in this study
2. Males or females, age 18-75 years, inclusive, at the Screening Visit
3. Total body weight >40 kg (88 lb)
4. Diagnosis of plaque psoriasis for ≥ 6 months
5. Plaques covering $\geq 10\%$ of body surface area (BSA)
6. Psoriasis area severity index (PASI) score ≥ 12 and static Physician's Global Assessment (sPGA) score ≥ 3
7. Women of childbearing potential (WOCBP) must agree to adhere to highly effective methods of contraception for the entirety of the study and for 30 days after the last dose of study drug
8. Males who are sexually active with WOCBP must agree to use highly effective methods of contraception for the entirety of the study and for 90 days after the last dose of study drug

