Appendix E Pruritus Numerical Rating Scale (NRS)

1. Numerical Rating Scale. On a scale from 0 (no itch) to 10 (worst imaginable itch)...

...how was your itch, on average, within the past 24 hours? Please select one number.

 0	 1	 2	 3	 4	 5	 6	 7	 8	 9	 10
----------------------------	----------------------------	----------------------------	----------------------------	----------------------------	----------------------------	----------------------------	----------------------------	----------------------------	----------------------------	-----------------------------

...how was your worst itch in the past 24 hours? Please select one number.

 0	 1	 2	 3	 4	 5	 6	 7	 8	 9	 10
----------------------------	----------------------------	----------------------------	----------------------------	----------------------------	----------------------------	----------------------------	----------------------------	----------------------------	----------------------------	-----------------------------

Phan NQ et al. Acta Derm Venereol. 2012;92:502-7

[figure not shown]
Verwegen E et al. Acta Derm Venereol. 2019;99:657-66

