5 GENERAL STATISTICAL CONSIDERATIONS

The primary analysis for the efficacy endpoints will be conducted using data collected through the 12-week treatment period. Data will be cleaned and locked prior to conducting the primary analysis.

The final analysis will be conducted after all subjects have completed their Week 16 or end of study (EOS) visit and after all study data is cleaned and locked.

SAS® version 9.4 or higher will be used for statistical analyses, tabulations, and graphical presentations.

In general, descriptive summaries will be presented by treatment groups (placebo and ESK-001 dose levels) and overall, for values at each visit. The descriptive summary for continuous variables will also be provided for the change from baseline and, if appropriate, for the change from week 12 to week 16. Summaries of continuous variables will include the number of subjects (N), mean, standard deviation (SD), median, Q1, Q3, minimum, and maximum. If there are variables with highly skewed distribution (e.g. log-normal distribution), then the geometric mean and %CV will also be reported in descriptive summaries. Inferential analysis for those variables may be performed after log-transformation as deemed appropriate. Descriptive summaries for categorical variables will include the number and percentage of subjects. Unless otherwise stated, denominators for percentages will be the number of subjects in the analysis population.

Between-group comparisons will focus on the comparative performance of a single ESK-001 dose versus placebo. All statistical tests will be conducted at a 2-sided significance level of 0.05. The corresponding p-values and two-sided 95% confidence intervals will be reported.

In general, baseline is defined as the last non-missing value prior to the first dose date and time. For subjects randomized but not dosed, the last non-missing value prior to the randomization date will be used as baseline. For any additional considerations, refer to each specific data section for details.

In general, efficacy data and other non-safety data will be presented by analysis visits as defined by the analysis visit window. Data collected at unscheduled or early termination (ET) visits will also be mapped to analysis visits as defined in [Appendix B](#). If a value does not fall within an analysis window, it will not be included in the summary analysis or comparative analysis.

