5.1 Analysis Populations

The following analysis populations are defined in this study:

- Modified Intent-to-Treat (mITT) Population: All randomized subjects who received at least one dose of study drug, with analyses conducted according to the assigned treatment. This will be the analysis population used for the primary efficacy analysis at Week 12.
- Intent-to-treat (ITT) Population: All randomized subjects, regardless of whether they receive study drug, with analyses conducted according to the assigned treatment.
- Per-protocol (PP) Population: All subjects in the ITT population who have received at least one dose of study drug as assigned, have both baseline and at least one post-baseline PASI score, and have no important protocol deviations (IPD) which may affect key primary and secondary efficacy endpoints in the treatment period.
- Safety Analysis Population: All randomized subjects who receive at least one dose of study drug with analyses conducted by actual treatment received.
- PK Analysis Population: All randomized subjects who receive at least 1 dose of ESK-001 and have at least one non-missing PK concentration with analysis conducted by actual treatment received.

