7 EFFICACY ANALYSES

All efficacy analyses will be conducted using the mITT Analysis Population. A sensitivity analysis using the ITT or PP analysis set may be performed as appropriate.

The primary and secondary endpoints are based on the efficacy response at the end of treatment (ie. Week 12).

In general, for responder type analyses, the difference in the proportion of subjects between two treatment arms at Week 12 or other timepoints (eg. Week 4, 8, if applicable) and the corresponding two-sided 95% CI will be calculated using the Fisher's exact test or the Chi-squared test depending on the number of observations (if cell counts are less than 5 then use Fisher's). A test of significance for the difference in proportion between two treatment groups will be performed using the Cochran Mantel-Haenszel (CMH) test adjusting for randomization stratification factors and the corresponding two-sided p-value will be presented.

A non-responder imputation will be applied to responder analyses in which subjects who drop out of the study before Week 12 will be considered as a non-responder at the week 12 visit. No imputation will be applied at any other post-baseline visits. [REDACTED]

For continuous efficacy measurements or scores, the treatment difference in the change from baseline between each active treatment and placebo will be compared using an ANCOVA model, with treatment group, visit and randomization stratification factors as fixed effects and baseline measure as a covariate. An unstructured covariance matrix will be used to model the correlation among repeated measurements (if convergence issues are encountered then compound symmetry covariance matrix will be used instead). Within-group least-squares (LS) means, standard errors (SEs), 2-sided 95% CIs, and p-values will be presented for Week 12 and other timepoints, if applicable.

Some efficacy analyses may also be presented by select subgroups of interest such as baseline PASI, age, BMI, race, gender and prior biologic use categories (refer to [Section 5.2](#)). However, given the small sample size, test for statistical significance will not be conducted for subgroup analyses.

[REDACTED]

[REDACTED]

[REDACTED]

[REDACTED]

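### The itch NRS and DLQI responder analyses in SAP 7.5 set no baseline condition, so subjects already below the cut-off can count as responders without improving

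*SAP*

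**What the plan says.** SAP 7.5 (Patient-Reported Outcomes) follows the change-from-baseline analyses with two responder analyses. For the DLQI, "a responder is defined as the subject who achieved a post-baseline score of 0 or 1". For the itch scale, "a responder is defined as a subject who has achieved a post-baseline itch score of < 4". Both rules look only at the post-baseline score.

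The denominator comes from elsewhere in the SAP:

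- SAP 7: "All efficacy analyses will be conducted using the mITT Analysis Population".
- SAP 5.1 defines that set as "All randomized subjects who received at least one dose of study drug, with analyses conducted according to the assigned treatment". It needs no baseline DLQI or itch value.
- SAP 5: unless otherwise stated, "denominators for percentages will be the number of subjects in the analysis population".

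On entry, Protocol 5.2 sets severity floors of BSA 10%, PASI 12 and "static Physician's Global Assessment (sPGA) score ≥ 3", but none for itch or DLQI. The itch items in Protocol Appendix E run from 0 to 10, so a baseline score of 0 to 3 is possible. The Protocol's Schedule of Assessments collects both questionnaires on Day 1.

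**The concern.** A subject who enters with itch 2 or DLQI 1 and does not change is counted as having achieved response, in any arm. The reported rate then combines two different things: reaching a low score from a higher one, and staying at a low score. A reader of the results table will take it as the first.

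The plan's other responder endpoints do not have this problem. The PASI responses require a percentage reduction from baseline, and sPGA 0/1 is protected by the sPGA entry floor. For the two patient-reported responders, nothing visible corrects for baseline. The CMH test adjusts only for the randomization factors, baseline score enters only the ANCOVA for continuous measures, and the SAP 5.2 subgroups include no baseline itch or DLQI category.

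At stake are how these rates can be interpreted and, under some conditions, the size of the treatment difference and the power to show it.

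**Working it through.** **The plan's own figure.** SAP 4 states at least 99% power for PASI-75 at 60% vs 10%, 35 per arm, two-sided 0.05. A pooled two-proportion calculation gives 99.8%, so the stated figure reproduces. The documents give no power or sample-size figure for the itch or DLQI responders.

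**Inputs.** From the documents: 35 per arm and two-sided alpha 0.05. Assumed, because the documents give no values:

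- f, the share per arm already below the cut-off at baseline: 2% to 30%.
- Response among the remaining subjects: pA = 60% active, pP = 20% placebo.
- Persistence, the proportion of low-baseline subjects counted as below the cut-off at Week 12: sA active, sP placebo.

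**Formula.** Observed rate in an arm = f × s + (1 − f) × p. Therefore

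observed difference = (1 − f)(pA − pP) + f(sA − sP).

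The difference is diluted only if sA − sP is smaller than pA − pP. If sA = sP, it is exactly (1 − f) times the difference among subjects above the cut-off.

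**Everyone below the cut-off stays there (sA = sP = 1).** At f = 10%, placebo is 0.10 + 0.90 × 0.20 = 28% and active is 0.10 + 0.90 × 0.60 = 64%, a difference of 36 points. At f = 30%, placebo is 0.30 + 0.70 × 0.20 = 44% and active is 0.30 + 0.70 × 0.60 = 72%, a difference of 28 points. Power below is for the pooled chi-square test, found by summing exact binomial probabilities over the rejection region. It ignores stratification.

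| f | Rates, all mITT | Difference | Power, n = 35 | Restricted n per arm | Power, restricted (60% vs 20%) |
|---|---|---|---|---|---|
| 0% | 60% vs 20% | 40.0 | 94% | 35 | 94% |
| 2% | 60.8% vs 21.6% | 39.2 | 93% | 34 | 94% |
| 5% | 62% vs 24% | 38.0 | 91% | 33 | 94% |
| 10% | 64% vs 28% | 36.0 | 86% | 32 | 93% |
| 30% | 72% vs 44% | 28.0 | 66% | 24 | 84% |

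Restricted n is 35 × (1 − f), rounded. Under this persistence assumption, restriction gains power despite the smaller denominator.

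**Sensitivity to the response rates.** At 50% vs 20% and f = 20%, with full persistence, the difference is 0.80 × 30 = 24 points and power (normal approximation) is 52% in all mITT, against 30 points and 66% when restricted to 28 per arm.

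**Sensitivity to persistence** (60% vs 20%, f = 20%):

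- 95% active vs 80% placebo: 0.80 × 40 + 0.20 × 15 = 35 points, power 83%. Some dilution remains.
- 95% active vs 60% placebo: 0.80 × 40 + 0.20 × 35 = 39 points, power 91%, against 88% restricted to 28 per arm. Dilution has all but gone, and the restricted analysis is slightly weaker.

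**The case against.** **These analyses are low in the hierarchy.** This stands. Neither responder analysis is a listed endpoint. The listed DLQI (secondary) and NRS (exploratory) endpoints are change from baseline, analysed by ANCOVA with baseline as covariate. The sample size rests on PASI-75 alone, so no stated power target is missed.

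**The size is assumed.** This also stands. One range for f should not serve both cut-offs. Itch below 4 covers 4 of 11 scale points, whereas DLQI 0/1 is the floor of a ten-item questionnaire in patients with PASI of at least 12. A low baseline is probably rarer for DLQI, though that is inference.

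**Dilution is not assured.** A reader might infer that low-baseline subjects cannot fail and that the difference must shrink. The documents do not support this. Treatments that could affect psoriasis are barred during the study (Protocol 6.12.2), so placebo subjects may worsen past the cut-off. In addition, "subjects who drop out of the study before Week 12 will be considered as a non-responder at the week 12 visit", so a low-baseline subject who drops out does not count as a responder. If these losses differ enough between arms, dilution disappears.

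**Chance imbalance.** A reader might also infer that unequal numbers of low-baseline subjects across 35-patient arms bias the comparison. Under randomization such imbalance is ordinary sampling error and leaves the test valid.

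**The all-mITT rate answers a fair question**, namely what share of subjects has little burden at Week 12. That is a reason to keep it, but not to let it stand alone as a measure of response.

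**Redaction.** Parts of SAP 7 are blacked out, one directly after the imputation rule. A baseline restriction there cannot be excluded, but the visible definitions in SAP 5.1 and 7.5 contain none.

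**Conclusion.** The point holds as a gap in two definitions. As written, a subject below the itch or DLQI cut-off at entry who stays there counts as a responder, so each rate mixes maintenance with response. This follows from the visible text for any share above zero.

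The effect on the treatment difference is conditional. If low-baseline subjects mostly stay low in both arms, the difference shrinks by about their share. Under 60% vs 20%, power falls from 94% to 86% at a 10% share and 66% at 30%, against 93% and 84% when restricted. At 2% to 5% the loss is about 1 to 4 points, which may be all that is at issue for DLQI. With persistence of 95% vs 60%, there is almost no dilution. The shares, response rates and persistence are all assumptions.

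The primary endpoint and the listed change-from-baseline endpoints are unaffected. This is a worthwhile, cheap correction to additional analyses, and it matters mainly for itch.

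**What to change.** Before unblinding, add to SAP 7.5:

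- The NRS responder analysis is done in mITT subjects with a baseline score of at least 4 on the item analysed (average or worst itch, each with its own denominator).
- The DLQI 0/1 analysis is done in mITT subjects with a baseline DLQI of at least 2.
- The number excluded is reported by arm, with missing baseline shown separately.
- The all-mITT version is kept as supportive and described as the proportion at or below the threshold, whatever the baseline score.

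The restriction uses only baseline data already scheduled for collection. If the redacted part of SAP 7 already contains it, a cross-reference in 7.5 is enough.

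The cost is a few SAP sentences and an extra table per analysis. The downside is a smaller denominator that differs by item, and thinner CMH strata. With four strata (prior biologics by region), 24 to 32 subjects per arm average 24/4 = 6 to 32/4 = 8 per arm per stratum.

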8 SAFETY ANALYSES

All safety analyses will be performed on the Safety Analysis Population and will be presented by each treatment group and the combined active treatment. In general safety data will be presented by descriptive statistics only and by nominal visit (if applicable). Safety data collected on unscheduled visits will be presented in listings only.

The treatment emergent period is defined as first dose through the end of study for subjects who complete the full treatment period of 12 weeks. If a subject discontinues study drug early, then the treatment emergent period will be first dose through four weeks after last dose.

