However, these values will be included in data listings and SAS data sets. When more than 1 value is available within the same analysis visit, the value collected closest to the target visit day will be used for analysis. If 2 values are equidistant to a target visit day (for example, 1 value is before and the other value is after the target day), then the value from the later date will be used for analysis.

Safety lab, ECG and PK data will be summarized by the nominal visit (per protocol). Unscheduled visits will be presented in listings only.

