8.1 Adverse Events

AEs will be coded to MedDRA version 25.0. AEs will be presented by SOC and PT, unless otherwise noted, in order of descending frequency on the overall total, and multiple occurrences of the same event in the same participant will be counted only once in the tables.

The following summaries of AEs will be provided:

- Overall summary of TEAEs
- All TEAEs
- Study drug related TEAE
- TEAEs by severity
- Grade 3 or higher TEAE
- Serious TEAEs (SAEs)
- Study drug-related SAEs
- TEAE leading to treatment discontinuation
- TEAE leading to death

By-subject listings of all AEs, SAEs, TEAEs leading to treatment discontinuation, TEAE leading to death will also be provided.

8.2 12-lead Electrocardiogram

12-lead electrocardiogram (ECG) data will be measured and read by local and central laboratory, and will be summarized for all subjects in the Safety Analysis Population.

8.2.1 *ECG Numeric Variables*

HR, PR, QRS, and Fridericia-corrected QT (QTcF) interval based on central ECG read and changes from baseline will be summarized by treatment group using descriptive statistics. The change from baseline of these ECG parameters at each time point will be listed for each subject.

8.2.2 *Categorical Analysis*

The number and percentage of subjects with maximum treatment-emergent post-dose QTcF values based on central ECG read in the following mutually exclusive categories will be summarized by treatment group: > 450 msec, > 480 msec, > 500 msec, > 520 msec, and > 550 msec. The number and percentage of subjects with maximum post-dose QTcF increase from baseline of > 30 msec and > 60 msec (mutually exclusive) will be summarized by treatment group.

Clinical significance will be summarized by treatment group and overall for the local and central ECG reads separately.

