8.3 Safety Laboratory Data

Safety laboratory data and change from baseline will be summarized by treatment group and visit using descriptive statistics.

Laboratory parameters that are graded in CTCAE Version 4.03 will be summarized by CTCAE grade. In the summary of laboratory parameters by CTCAE grade, for parameters with CTCAE grading in both high and low direction (e.g., calcium, glucose, magnesium, potassium, sodium), CTCAE in high and low directions will be summarized separately. Subjects with treatment-emergent laboratory abnormalities of Grade 3 or higher will also be summarized. Shift from baseline to the worst post-baseline CTC grade of Grade 3 or higher will also be presented for select laboratory tests of interest including neutrophils, platelets, hemoglobin, creatine kinase, AST, ALT, total bilirubin, triglycerides, and cholesterol.

Absolute values over time will also be plotted for select laboratory tests of interest including neutrophils, platelets, hemoglobin, creatine kinase, AST, ALT, total bilirubin, triglycerides, and cholesterol. Listings of laboratory values will be generated and the results that are out of the reference range will be flagged.

8.3.1 *Potential Drug-induced Liver Injury*

The liver function tests, namely alanine aminotransferase (ALT), aspartate aminotransferase (AST), alkaline phosphatase (ALP), and total bilirubin (TBL) are used to assess possible drug - induced liver injury (DILI).

A graph of distribution of peak values of ALT versus peak values of TBL will be presented. ALT and TBL values will be presented on a logarithmic scale. The graph will be divided into

4 quadrants with a vertical line corresponding to $3 \times$ the upper limit of normal (ULN) for ALT and a horizontal line corresponding to $2 \times$ ULN for TBL.

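### The SAP's listings-only rule for unscheduled safety data is not limited to by-visit summaries and, as written, clashes with its own subject-level safety outputs

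*SAP*

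**What the plan says.** Two sentences set the rule. SAP 5, straight after placing laboratory, ECG and PK results on nominal visits, says "Unscheduled visits will be presented in listings only". SAP 8, after a similar sentence about safety data in general, says "Safety data collected on unscheduled visits will be presented in listings only". Neither sentence carries an exception.

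The sections that follow define several outputs by subject. SAP 8.2.2 tabulates "The number and percentage of subjects with maximum treatment-emergent post-dose QTcF values based on central ECG read" by category, and also the "maximum post-dose QTcF increase from baseline of" more than 30 or 60 msec. SAP 8.3 adds "Subjects with treatment-emergent laboratory abnormalities of Grade 3 or higher will also be summarized" and, for selected tests, an output described as "Shift from baseline to the worst post-baseline CTC grade of Grade 3 or higher". SAP 8.3.1 plots peak ALT against peak total bilirubin, counts subjects with liver test elevations in the treatment-emergent period, classifies whether those elevations normalised, and counts potential Hy's law cases using the order of the transaminase and bilirubin elevations.

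The treatment-emergent period in SAP 8 is a span of time, not a set of visits. For subjects who complete 12 weeks of treatment it runs from first dose to end of study.

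On the protocol side, section 10.4.3 counts patients with any postdose QTcF above 450, 480 or 500 msec. Section 8.3.2 lets the investigator order safety laboratory tests at unscheduled times. Section 8.3.1.3 asks for abnormal results to be retested as clinically indicated. The schedule in section 1.3 has an unscheduled-visit column in which blood count, chemistry and ECG are marked.

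**The concern.** A maximum, peak or worst grade taken over scheduled visits alone is not the treatment-emergent or post-baseline extreme that the SAP names. Unscheduled tests may be ordered because something looked wrong, so the values left out need not resemble those kept in.

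If the rule is programmed as written, a subject whose only qualifying value was unscheduled drops out of the QTcF, Grade 3 or higher, or liver table, or is placed in a milder category. A subject whose recovery was documented only by a repeat test could be shown as never normalised. Two programmers following the same SAP could produce different tables, and the SAP does not say which is right. The five dose arms will be compared on these tables.

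**Working it through.** No figure in the documents is at issue, so the check sets the texts side by side.

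**1. Is the rule limited anywhere?** In SAP 8 the softening words (in general; if applicable) belong to the preceding sentence about nominal visits, not to the sentence about unscheduled data. SAP 5 does say how unscheduled efficacy values enter the analysis: they are mapped to analysis visits. For safety values the only stated treatment is a listing. SAP 8.2.2, 8.3 and 8.3.1 contain no readable exception.

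**2. Which outputs are touched?**

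| Output | SAP section | Defined over | Effect of dropping unscheduled values |
|---|---|---|---|
| Maximum QTcF | 8.2.2 | treatment-emergent, post-dose | lower category, or out of the table |
| Maximum QTcF increase | 8.2.2 | post-dose | same |
| Grade 3 or higher laboratory abnormality | 8.3 | treatment-emergent | subject may not be counted |
| Worst CTC grade shift | 8.3 | post-baseline | milder grade |
| Peak ALT against peak bilirubin | 8.3.1 | peak per subject | point may fall in a lower quadrant |
| Liver elevation | 8.3.1 | treatment-emergent period | lower category, or not counted |
| Normalisation | 8.3.1 | values after the elevation | recovery may go unseen |
| Potential Hy's law | 8.3.1 | order of the elevations | order may change or be lost |

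The numeric summaries of ECG, laboratory and vital sign values by visit are not in conflict with the rule.

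**3. Which way does the error run?** Let S be a subject's scheduled values and U the unscheduled values in the period an output covers. Then max(S) ≤ max(S ∪ U). The number of subjects above any threshold can therefore only stay the same or fall when U is dropped. The protocol's count of any postdose QTcF above a threshold has the same form, so it too can only shrink. Among subjects whose elevation is counted, and if any later return to normal counts as normalisation, the never-normalised number can only stay the same or rise. The Hy's law count is likely to fall, for example when the transaminase elevation that preceded a bilirubin elevation was seen only at an unscheduled visit. It is not bound to fall, because dropping a value can also change the apparent order.

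**4. Will such values exist?** The documents foresee them: investigator-ordered laboratory tests (Protocol 8.3.2), repeat tests (Protocol 8.3.1.3), and the unscheduled column for blood count, chemistry and ECG (Protocol 1.3). They give no frequency, so no expected count can be derived.

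**5. Scale of one subject.** With 35 per arm (SAP 4), 1/35 = 2.9 percentage points. The five active arms together have 5 × 35 = 175, and 1/175 = 0.6 percentage point. This is the weight of any one subject in these tables, not an estimate of the effect.

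**The case against.** The best defence is context. Both sentences follow statements about nominal visits, and a specific output definition normally governs a general presentation rule. A fully literal reading would even remove adverse events collected at unscheduled visits from the table of all TEAEs, which nobody can have intended. So the by-visit reading is the likely intent. This stands, and it makes the point one of drafting rather than a plan to suppress data. It does not supply the missing limit.

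Mitigation also stands in part. Clinically significant laboratory abnormalities that need active management are recorded as adverse events (Protocol 8.3.1.3) and so can enter the TEAE tables. SAP 8.3 promises "Listings of laboratory values will be generated and the results that are out of the reference range will be flagged". The protocol's own liver injury output, and its output for QTcF above 520 msec, are listings. The safety monitoring committee reviews safety data. A repeat test often follows a scheduled abnormality that is already counted, and then only its category, normalisation or order is at risk. None of this puts an unscheduled value into the QTcF, laboratory or liver tables or the ALT/bilirubin plot.

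Three stronger readings are tempting, and the documents do not support them.

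- A reader might infer that early termination values are excluded too. The rule names unscheduled visits only. The schedule gives early termination its own column, and SAP 5 names the two separately.
- A reader might infer that normalisation is cut off for early discontinuers, because SAP 8 says "If a subject discontinues study drug early, then the treatment emergent period will be first dose through four weeks after last dose". In SAP 8.3.1 that period is attached to the elevation. No text confines normalisation to it, and one of the listed categories is normalisation after permanent discontinuation.
- A reader might infer that the SAP contains no exception at all. Parts of SAP 5.5 and SAP 7 are redacted, so only the absence of a readable exception can be claimed. The visible text around those gaps does not deal with unscheduled safety data.

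**Conclusion.** The point holds as a conflict of scope. The listings-only rule is stated twice without a readable limit, and applied as written it gives wrong results for the subject-level safety outputs in SAP 8.2.2, 8.3 and 8.3.1 and narrows the QTcF count in Protocol 10.4.3. Threshold counts could be understated and never-normalised overstated.

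Whether this happens depends on how the rule is programmed, which the documents do not settle. How much it matters depends on how many subjects have a decisive value only at an unscheduled visit, which the documents do not let us estimate. The documents do not show that any count will in fact be wrong. The change should be made before unblinding, because it is cheap and removes a choice that should not be made after the data are seen.

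**What to change.** In SAP 5 and SAP 8, state three things:

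- The listings-only rule applies to by-visit summaries only.
- Adverse event summaries are not affected.
- Subject-level outputs (maximum QTcF, maximum QTcF increase, Grade 3 or higher laboratory abnormalities, worst grade, peak ALT and bilirubin, liver elevation, normalisation and potential Hy's law) use all available values, including unscheduled ones, within the period each output already defines.

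SAP 8.3.1 states no period for the peak plot or the Hy's law count. That is a separate drafting matter, which this change neither depends on nor settles.

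The cost is one or two sentences, a flag in the analysis datasets and minor programming. By-visit tables stay as planned. Some abnormality counts may become slightly less favourable.
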